This parametric comparative trial will randomly assign 140 inner-city adolescents with ADHD to (1) CASH-AA Only or (2) CASH-AA + MIP. Treatment will occur in community behavioral health clinics. All participants will receive behavioral interventions (CASH-AA): family psychoeducation in ADHD symptoms, executive functioning, and developmental impacts; family-based motivation and ADHD accommodation interventions; and academic training focused on home environment support and organizational skills. Half of the participants

will also receive medication decision-making interventions (MIP): ADHD medication psychoeducation, family decision-making interventions, and (for those who elect to start medication) coordinated medication management. Half of the sample will have comorbid substance use problems. Treatment will occur in three community clinics; therapists will be randomly assigned to study condition. Caregivers and adolescents will complete assessments at baseline, 3, 6, and 12-month follow-up. Multilevel modeling will compare the effectiveness of each condition on key patient and service use outcomes. Patient-centered analyses will explore differential treatment effects based on (a) Medication decision (yes/no); (b) Substance use comorbidity (yes/no); (c) Race/Ethnicity (Hispanic, African American).

Quantitative outcome analyses will test for service use effects, symptom reduction, and quality of life improvements that are primary reasons for seeking clinical services. Qualitative interviews will document family-specific rationale for decisions about medication, compliance with behavioral and medication interventions, and suggestions for improving services and service integration. Note that families assigned to CASH-AA Only will retain the option of pursuing ADHD medication through treatment-as-usual procedures at their respective clinic. Similarly, families assigned to CASH-AA + MIP will not be required to start ADHD medication. Instead, they will receive informed-choice interventions and can choose when and if to start medication; the study will assess the impact of these decisions on clinical outcomes.

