Hypothesis 3: Better Treatment Attendance. Integrated clients will attend more behavioral therapy sessions and medication management sessions than Behavioral Only clients.

Hypothesis 4: Greater Medication Acceptance and Treatment Satisfaction. Integrated clients will more often consent to medication, show greater medication compliance, and report greater overall satisfaction than Behavioral Only.

Aim 3: Examine Patient-Centered Outcomes

Research Question 1: Heterogeneity of Treatment Effects. Will clients with co-occurring substance use problems have worse treatment outcomes than those without? Will there be outcome differences based on age, ethnicity, sex?

Research Question 2: Analysis of Individual Differences. Across treatment conditions, will clients who choose to start a medication regimen have better treatment outcomes than those who do not?

Study Design

This study emphasizes ecological validity: Both protocols will be implemented in existing outpatient behavioral services by agency clinicians. To promote internal validity, randomization will occur within site at both the client and therapist level (i.e., study therapists at

each site will be randomly assigned to condition). The primary benefit of “doubly randomized” designs is that they minimize potential bias related to site effects—because randomization occurs within each site—and therapist sampling bias—because therapists are randomly assigned to condition. The use of a Behavioral Only condition will control treatment expectancy effects. Therapists will be trained and supervised to implement CASH-AA and MIP as part of their otherwise routine duties; that is, the protocols will be additional components of their usual practice for study cases. To maximize protocol exposure, and to promote consistency in the timing of protocol implementation across conditions and cases, therapists will be asked to implement CASH-AA and MIP at the start of treatment (unless contraindicated).

Note: (1) ADHD medication will be available to all Behavioral Only cases via routine site practices for ADHD treatment; and (2) MIP supports family decision-making about medication but does not require families to start a medication regimen.

Sample Description

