As occurred during the pilot tests of the MIP and CASH-AA protocols, the proposed study will provide on-site training in CASH-AA (3 hours) to all study therapists, led by study investigators. Study investigators will then continue training therapists in the Integrated condition in MIP (additional 3 hours). After initial training, two separate monthly fidelity monitoring meetings will occur at each site, one for each study condition. Ad hoc training will be provided to new therapists whenever there is staff turnover.

Fidelity monitoring (FM) meetings will be organized using principles of localized quality assurance procedures for promoting the sustainability of evidence-based practices in usual care. Specifically, FM meetings will feature data from the therapist-report CASH-AA and MIP fidelity measures, along with a therapist-report measure of evidence-based practices for adolescent

conduct and substance use problems, as quality assurance tools and clinical supervision aids. Also, over the course of the study FM meetings will follow a multistep process to develop on-site clinical expertise and incrementally increase on-site supervision responsibilities in proportion to decreased extramural involvement.

Study Measures

Client Demographics, Multidomain Risk Factors, and Psychiatric Diagnoses

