Client research interviews (phone screen, baseline interview, and 3-, 6- and 12-month follow-up interviews) will be conducted by research staff primarily in the home or site clinical offices but also in other locations upon request. Caregivers and teens will be consented and interviewed separately; caregivers will consent for themselves and for their adolescents, and adolescents will assent for themselves. Recruitment procedures, randomization procedures, and assessment measures and procedures are fully described above. Caregiver consents and assessments will be administered in the preferred language: English or Spanish. Many assessment measures have Spanish versions available from the vendor; all other measures, and all consents, will be translated by a professional translation agency using back-translation techniques that are high-standard methods in the field. Clients will be fully informed about the general treatment services to be offered—with at least some focus on attention and impulsivity problems—and about randomization procedures prior to consenting to participate, in the following manner: “You and your teen agree to enter a lottery at the counseling program. Half of families in the study will be assigned to therapists who will use research tools to educate their clients about attention problems in adolescents, and half will be assigned to therapists who will use their regular procedures to educate clients. All study families will receive the same access to

all available services at the clinic.” Research staff will give a copy of the consent/assent form (consent/assent to participate in the study; consent/assent to audiotape sessions) to caregivers and adolescents, read them aloud, and then ask family members if they have any questions, clarifications, or concerns before signing. After consenting/assenting to study participation and completing the Baseline interview, families will then be linked to services at a partnering treatment site by research staff using intensive family-based engagement strategies (also described above). Caregivers will receive \$25 in vouchers for completing the Phone Screen, and caregivers and adolescents will each receive \$40 for completing the Baseline interview, \$50 apiece for the first two follow-ups, and \$100 apiece for the final follow-up interview

Site Therapists

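### The consent script describes a regular-procedures half that the design does not contain, and does not mention MIP, the only randomized difference

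*Combined protocol and SAP*

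**What the plan says.** Under Procedures For Obtaining Informed Consent (Clients: Caregivers and Adolescents), the protocol states an aim, "Clients will be fully informed about the general treatment services to be offered", extends it to the randomization procedure, and then gives the words to be used. Families agree to a lottery. Of one group the script says that "half will be assigned to therapists who will use their regular procedures to educate clients". The other group it describes in these terms: "Half of families in the study will be assigned to therapists who will use research tools to educate their clients about attention problems in adolescents". The script closes by promising all study families equal access to the clinic's services. Staff also hand over the consent and assent forms, read them aloud and take questions.

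The design is set out elsewhere. The Project Abstract says the trial will "randomly assign 140 inner-city adolescents with ADHD to (1) CASH-AA Only or (2) CASH-AA + MIP". It adds: "All participants will receive behavioral interventions (CASH-AA): family psychoeducation in ADHD symptoms, executive functioning, and developmental impacts". Therapist Training and Fidelity Monitoring Procedures says the study "will provide on-site training in CASH-AA (3 hours) to all study therapists", and that therapists in the Integrated condition then have a further 3 hours on MIP. The section on risks for therapists has CASH-AA fidelity reported in both conditions and MIP fidelity in the Integrated condition only.

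**The concern.** The script is the only account in the documents of what families hear about the arms, and it presents a contrast between a study treatment and usual practice. The trial compares two study treatments, one of which adds support for decisions about medication. A family relying on the script would misunderstand what the lottery decides.

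By the protocol's own account the omission matters to these families. Study Purpose And Aims says that families in specialty care consistently prefer behavioral services alone. The Project Abstract names stigma and misinformation among the reasons that ADHD medication is little used. The risk section sets out the general risks of medication because MIP helps families decide about it. Assignment to a medication decision protocol is therefore something a family could reasonably want to know before agreeing. The documents give no reason for a partial description of the arms and describe no later debriefing.

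**Working it through.** The plan has no calculated figure to reproduce here. The check sets the script beside the arm definitions.

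Inputs:
- Planned sample: 140 (Project Abstract).
- Share in each arm of the lottery: one half, both in the script and in the Project Abstract's statement of who also receives MIP. An exact even split is assumed; the urn scheme need not give exactly 70.
- Who receives CASH-AA: all participants (Project Abstract).
- Whether CASH-AA teaches about ADHD: yes, ADHD psychoeducation is one of its three listed components (Project Abstract).
- Who is trained in CASH-AA: all study therapists. The Behavioral Only description under Study Conditions says separately that its therapists are trained and monitored in it.

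| | As the script has it | As the design has it |
|---|---|---|
| Families taught about attention problems or ADHD with a study protocol | 140 × 1/2 = 70 | 140 × 1 = 140 |
| Families taught by regular procedures instead | 140 − 70 = 70 | 140 − 140 = 0 |
| Families assigned to MIP | not mentioned | 140 × 1/2 = 70 |

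The one-half in the script corresponds to only one thing in the design, assignment to MIP, and the script neither names MIP nor refers to medication.

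A kinder reading is possible: research tools could mean MIP, and regular procedures could mean the clinic's routine handling of medication. The wording does not allow it. The script speaks of educating clients about attention problems, and CASH-AA does that in both arms.

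On reach, families consent before the intake interview and are randomized after it. The script is therefore meant for at least the 140 families later randomized, and also for any who consent but do not complete intake.

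**The case against.** Several points on the other side stand.

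- **The forms are unseen.** The consent and assent forms are given out and read aloud, and their text is not in the documents. Baseline Eligibility Interviews and Consent into the Follow-Up Study describes a further consent, which covers enrollment at a site trained in both MIP and CASH-AA, with questions answered afterwards. A reader might infer that medication decision support is never disclosed to families. The documents do not support that; they show only that the quoted script omits it.
- **The script is not wholly false.** Both arms receive routine site services, and on medication the Behavioral Only arm does follow site routine, which the study tracks but does not direct. The promise of equal access agrees with the Study Design note that medication is available to Behavioral Only families through the clinic. A reader might say that families enter a lottery between arms that do not exist, but that goes too far. The error is in leaving CASH-AA out of one half and MIP out of the other.
- **The safety consequence is limited.** No family is required to start medication, and site psychiatrists are to review safety information with adolescent and caregiver before prescribing.

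A reader might also take the script as evidence against the Study Design statement that "The use of a Behavioral Only condition will control treatment expectancy effects". The documents do not support that step. A comparator that is itself an active study protocol is an ordinary partial control of expectancy. The difference of 3 hours against 3 + 3 = 6 hours is in therapist training, not in client contact, and sites prescribe weekly sessions for all cases. An accurate script would not remove an expectancy difference and could make the contrast between arms more visible. Expectancy control is therefore not part of this point.

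None of this reconciles the script with the design. If the forms describe the arms correctly, families would receive two incompatible accounts.

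**Conclusion.** The concern holds as a contradiction between the consent script and the arm definitions. The script places half the families with therapists using regular procedures to educate, where the design places none. It also leaves out MIP, the only randomized difference, to which about 70 of 140 families would be assigned on an even split. This is more than a clerical slip or a missing detail, since it is the wording by which families are to be fully informed and it is wrong as written.

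The conclusion rests on the script as quoted and on the arm definitions, which agree with one another wherever they appear. It makes no assumption about what the forms say. It concerns consent and internal consistency, and it changes no sample size, power or error rate.

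**What to change.** Rewrite the script so that it states what the protocol already says of the arms:
- all families receive the study's behavioral and academic protocol;
- half are assigned by lottery to therapists who also use a study protocol that helps families learn about and decide on ADHD medication;
- no family is required to start medication, and it is available through the clinic in both arms, as the Project Abstract and Study Design state.

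Check the consent and assent forms for the regular-procedures wording and for a description of MIP, and bring them into line with the script where they differ. The cost is one script amendment through the IRB, plus form changes if the check shows they are needed. Sample and analysis are unaffected.
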